Appendix 4 EORTC QLQ-Core 30 and Modified EORTC QLQ-BR23 Measures (cont.)

During the past week:	Not at All	A Little	Quite a Bit	Very Much
17. Have you had diarrhea?	1	2	3	4
18. Were you tired?	1	2	3	4
19. Did pain interfere with your daily activities?	1	2	3	4
20. Have you had difficulty in concentrating on things, like reading a newspaper or watching television?	1	2	3	4
21. Did you feel tense?	1	2	3	4
22. Did you worry?	1	2	3	4
23. Did you feel irritable?	1	2	3	4
24. Did you feel depressed?	1	2	3	4
25. Have you had difficulty remembering things?	1	2	3	4
26. Has your physical condition or medical treatment interfered with your family life?	1	2	3	4
27. Has your physical condition or medical treatment interfered with your social activities?	1	2	3	4
28. Has your physical condition or medical treatment caused you financial difficulties?	1	2	3	4

For the following questions please circle the number between 1 and 7 that best applies to you

29. How would you rate your overall health during the past week?

1 2 3 4 5 6 7

Very poor

Excellent

30. How would you rate your overall quality of life during the past week?

1 2 3 4 5 6 7

Very poor

Excellent

Appendix 4 EORTC QLQ-Core 30 and Modified EORTC QLQ-BR23 Measures (cont.)

Patients sometimes report that they have the following symptoms or problems. Please indicate the extent to which you have experienced these symptoms or problems during the past week.

During the past week:	Not at All	A Little	Quite a Bit	Very Much
31. Did you have a dry mouth?	1	2	3	4
32. Did food and drink taste different than usual?	1	2	3	4
33. Were your eyes painful, irritated or watery?	1	2	3	4
34. Have you lost any hair?	1	2	3	4
35. Answer this question only if you had any hair loss: Were you upset by the loss of your hair?	1	2	3	4
36. Did you feel ill or unwell?	1	2	3	4
37. Did you have hot flushes?	1	2	3	4
38. Did you have headaches?	1	2	3	4
39. Have you felt physically less attractive as a result of your disease or treatment?	1	2	3	4
40. Have you been feeling less feminine as a result of your disease or treatment?	1	2	3	4
41. Did you find it difficult to look at yourself naked?	1	2	3	4
42. Have you been dissatisfied with your body?	1	2	3	4
43. Were you worried about your health in the future?	1	2	3	4
44. Have you had skin problems (e.g. itchy, dry)?	1	2	3	4
45. Did itching of your skin bother you?	1	2	3	4
46. Have you had a sore mouth or tongue?	1	2	3	4
47. Have you had trouble swallowing?	1	2	3	4

Please go on to the next page

Appendix 4
EORTC QLQ-Core 30 and Modified EORTC QLQ-BR23 Measures
(cont.)

During the past four weeks:	Not at All	A Little	Quite a Bit	Very Much
48. To what extent were you interested in sex?	1	2	3	4
49. To what extent were you sexually active? (with or without intercourse)	1	2	3	4
50. Answer this question only if you have been sexually active: To what extent was sex enjoyable for you?	1	2	3	4

Appendix 5 New York Heart Association Classifications

Clinical Evaluation of Functional Capacity of Patients

NYHA	Functional Class	Description	Objective Assessment
I	Mild	No limitation of physical activity. Ordinary physical activity does not cause undue fatigue, palpitation or dyspnea.	No objective evidence of cardiovascular disease.
II	Mild	Slight limitation of physical activity. Comfortable at rest, but ordinary physical activity results in fatigue, palpitation or dyspnea	Objective evidence of minimal cardiovascular disease
III	Moderate	Marked limitation of physical activity. Comfortable at rest, but less than ordinary activity causes fatigue, palpitation or dyspnea.	Objective evidence of moderately severe cardiovascular disease.
IV	Severe	Unable to carry out any physical activity without discomfort. Symptoms of cardiac insufficiency at rest. If any physical activity is undertaken, discomfort is increased.	Objective evidence of severe cardiovascular disease.

Appendix 6 American Joint Committee on Cancer TNM Classification of Malignant Tumors

Tumor (T)

TX	Primary tumor cannot be assessed
T0	No evidence of primary tumor
Tis	Carcinoma in situ
Tis (DCIS)	DCIS
Tis (LCIS)	LCIS
Tis (Paget)	Paget disease of the nipple NOT associated with invasive carcinoma and/or carcinoma in situ (DCIS and/or LCIS) in the underlying breast parenchyma. Carcinomas in the breast parenchyma associated with Paget disease are categorized based on the size and characteristics of the parenchymal disease, although the presence of Paget disease should still be noted.
T1	Tumor ≤ 20 mm in greatest dimension
T1mi	Tumor ≤ 1 mm in greatest dimension
T1a	Tumor >1 mm but ≤ 5 mm in greatest dimension
T1b	Tumor >5 mm but ≤ 10 mm in greatest dimension
T1c	Tumor >10 mm but ≤ 20 mm in greatest dimension

Appendix 6 American Joint Committee on Cancer TNM Classification of Malignant Tumors (cont.)

Tumor (T)

T2	Tumor >20 mm but ≤50 mm in greatest dimension
T3	Tumor >50 mm in greatest dimension
T4	Tumor of any size with direct extension to the chest wall and/or to the skin (ulceration or skin nodules) ^a
T4a	Extension to the chest wall, not including only pectoralis muscle adherence/invasion
T4b	Ulceration and/or ipsilateral satellite nodules and/or edema (including peau d'orange) of the skin, which do not meet the criteria for inflammatory carcinoma
T4c	Both T4a and T4b
T4d	Inflammatory carcinoma

Reprinted with permission from AJCC: Breast. In: Edge SB, Byrd DR, Compton CC, et al., eds.: AJCC Cancer Staging Manual. 7th ed. New York, NY: Springer, 2010, pp 347–76.

DCIS = ductal carcinoma in situ; LCIS = lobular carcinoma in situ.

Note: The T classification of the primary tumor is the same regardless of whether it is based on clinical or pathologic criteria, or both. Size should be measured to the nearest millimeter. If the tumor size is slightly less than or greater than a cut-off for a given T classification, it is recommended that the size be rounded to the millimeter reading that is closest to the cut-off. For example, a reported size of 1.1 mm is reported as 1 mm, or a size of 2.01 cm is reported as 2 cm. Designation should be made with the subscript "c" or "p" modifier to indicate whether the T classification was determined by clinical (physical examination or radiologic) or pathologic measurements, respectively. In general, pathologic determination should take precedence over clinical determination of T size.

^a Invasion of the dermis alone does not qualify as T4.

Appendix 6
American Joint Committee on Cancer TNM Classification of Malignant Tumors (cont.)

Regional Lymph Nodes (N)

Clinical	
NX	Regional lymph nodes cannot be assessed (e.g., previously removed)
N0	No regional lymph node metastases
N1	Metastases to movable ipsilateral level I, II axillary lymph node(s)
N2	Metastases in ipsilateral level I, II axillary lymph nodes that are clinically fixed or matted
	OR Metastases in clinically detected ^a ipsilateral internal mammary nodes in the absence of clinically evident axillary lymph node metastases
N2a	Metastases in ipsilateral level I, II axillary lymph nodes fixed to one another (matted) or to other structures
N2b	Metastases only in clinically detected ^a ipsilateral internal mammary nodes and in the absence of clinically evident level I, II axillary lymph node metastases
N3	Metastases in ipsilateral infraclavicular (level III axillary) lymph node(s) with or without level I, II axillary lymph node involvement
	OR
	Metastases in clinically detected ^a ipsilateral internal mammary lymph node(s) with clinically evident level I, II axillary lymph node metastases
	OR
	Metastases in ipsilateral supraclavicular lymph node(s) with or without axillary or internal mammary lymph node involvement
N3a	Metastases in ipsilateral infraclavicular lymph node(s)

Appendix 6 American Joint Committee on Cancer TNM Classification of Malignant (cont.)

Regional Lymph Nodes (N)

Clinical	
N3b	Metastases in ipsilateral internal mammary lymph node(s) and axillary lymph node(s)
N3c	Metastases in ipsilateral supraclavicular lymph node(s)

Reprinted with permission from AJCC: Breast. In: Edge SB, Byrd DR, Compton CC, et al., eds.: AJCC Cancer Staging Manual. 7th ed. New York, NY: Springer, 2010, pp. 34776.

^a Clinically detected is defined as detected by imaging studies (excluding lymphoscintigraphy) or by clinical examination and having characteristics highly suspicious for malignancy or a presumed pathologic macrometastasis based on fine needle aspiration biopsy with cytologic examination. Confirmation of clinically detected metastatic disease by fine needle aspiration without excision biopsy is designated with an (f) suffix, for example, cN3a(f). Excisional biopsy of a lymph node or biopsy of a sentinel node, in the absence of assignment of a pT, is classified as a clinical N, for example, cN1. Information regarding the confirmation of the nodal status will be designated in site-specific factors as clinical, fine needle aspiration, core biopsy, or sentinel lymph node biopsy. Pathologic classification (pN) is used for excision or sentinel lymph node biopsy only in conjunction with a pathologic T assignment.

Appendix 6 American Joint Committee on Cancer TNM Classification of Malignant (cont.)

Pathologic (pN)¹

pNX	Regional lymph nodes cannot be assessed (e.g., previously removed or not removed for pathologic study)
pN0	No regional lymph node metastasis identified histologically

Note: ITCs are defined as small clusters of cells ≤ 0.2 mm, or single tumor cells, or a cluster of < 200 cells in a single histologic cross-section. ITCs may be detected by routine histology or by IHC methods. Nodes containing only ITCs are excluded from the total positive node count for purposes of N classification but should be included in the total number of nodes evaluated.
	
pN0(i-)	No regional lymph node metastases histologically, negative IHC
pN0(i+)	Malignant cells in regional lymph node(s) ≤ 0.2 mm (detected by H&E or IHC including ITC)
pN0(mol-)	No regional lymph node metastases histologically, negative molecular findings (RT-PCR)
pN0(mol+)	Positive molecular findings (RT-PCR), but no regional lymph node metastases detected by histology or IHC
pN1	Micrometastases
	OR
	Metastases in 1–3 axillary lymph nodes
	AND/OR
	Metastases in internal mammary nodes with metastases detected by sentinel lymph node biopsy but not clinically detected ^a
pN1mi	Micrometastases (> 0.2 mm and/or > 200 cells but none > 2 mm)
pN1a	Metastases in 1–3 axillary lymph nodes, at least one metastasis > 2 mm
pN1b	Metastases in internal mammary nodes with micrometastases or macrometastases detected by sentinel lymph node biopsy but not clinically detected ^a

Appendix 6 American Joint Committee on Cancer TNM Classification of Malignant (cont.)

Pathologic (pN)¹

pN1c	Metastases in 1–3 axillary lymph nodes and in internal mammary lymph nodes with micrometastases or macrometastases detected by sentinel lymph node biopsy but not clinically detected
pN2	Metastases in 4–9 axillary lymph nodes
	OR Metastases in clinically detected ^a internal mammary lymph nodes in the absence of axillary lymph node metastases
pN2a	Metastases in 4–9 axillary lymph nodes (at least 1 tumor deposit > 2 mm)
pN2b	Metastases in clinically detected ^d internal mammary lymph nodes in the absence of axillary lymph node metastases
pN3	Metastases in ≥ 10 axillary lymph nodes
	OR
	Metastases in infraclavicular (level III axillary) lymph nodes
	OR
	Metastases in clinically detected ^c ipsilateral internal mammary lymph nodes in the presence of one or more positive level I, II axillary lymph nodes
	OR
	Metastases in > 3 axillary lymph nodes and in internal mammary lymph nodes with micrometastases or macrometastases detected by sentinel lymph node biopsy but not clinically detected ^a
	OR Metastases in ipsilateral supraclavicular lymph nodes

Appendix 6 American Joint Committee on Cancer TNM Classification of Malignant (cont.)

Pathologic (pN)¹

pN3a	Metastases in ≥ 10 axillary lymph nodes (at least 1 tumor deposit >2 mm)
	OR
	Metastases to the infraclavicular (level III axillary lymph) nodes.
pN3b	Metastases in clinically detected ^b ipsilateral internal mammary lymph nodes in the presence of one or more positive axillary lymph nodes;
	OR
	Metastases in > 3 axillary lymph nodes and in internal mammary lymph nodes with micrometastases or macrometastases detected by sentinel lymph node biopsy but not clinically detected ^a
pN3c	Metastases in ipsilateral supraclavicular lymph nodes
Post-treatment ypN	
Post-treatment yp "N" should be evaluated as for clinical (pretreatment) "N" methods above. The modifier "SN" is used only if a sentinel node evaluation was performed after treatment. If no subscript is attached, it is assumed that the axillary nodal evaluation was by AND.	
The X classification will be used (ypNX) if no yp post-treatment SN or AND was performed	
N categories are the same as those used for pN	

Appendix 6

American Joint Committee on Cancer TNM Classification of Malignant (cont.)

AND= axillary node dissection; H&E= hematoxylin and eosin stain; IHC= immunohistochemical; ITC= isolated tumor cells; RT-PCR= reverse transcriptase/polymerase chain reaction.

Reprinted with permission from AJCC: Breast. In: Edge SB, Byrd DR, Compton CC, et al., eds.: AJCC Cancer Staging Manual. 7th ed. New York, NY: Springer, 2010, pp. 347–76.

¹ Classification is based on axillary lymph node dissection with or without sentinel lymph node biopsy. Classification based solely on sentinel lymph node biopsy without subsequent axillary lymph node dissection is designated (SN) for "sentinel node," for example, pN0(SN).

^a "Not clinically detected" is defined as not detected by imaging studies (excluding lymphoscintigraphy) or not detected by clinical examination.

^b "Clinically detected" is defined as detected by imaging studies (excluding lymphoscintigraphy) or by clinical examination and having characteristics highly suspicious for malignancy or a presumed pathologic macrometastasis based on fine-needle aspiration biopsy with cytologic examination.

Distant Metastases (M)

M0	No clinical or radiographic evidence of distant metastases
cM0(i+)	No clinical or radiographic evidence of distant metastases, but deposits of molecularly or microscopically detected tumor cells in circulating blood, bone marrow, or other non-regional nodal tissue that are ≤0.2 mm in a patient without symptoms or signs of metastases
M1	Distant detectable metastases as determined by classic clinical and radiographic means and/or histologically proven >0.2 mm

Reprinted with permission from AJCC: Breast. In: Edge SB, Byrd DR, Compton CC, et al., eds.: AJCC Cancer Staging Manual. 7th ed. New York, NY: Springer, 2010, pp. 347–76.

Post-treatment yp M classification. The M category for patients treated with neoadjuvant therapy is the category assigned in the clinical stage, prior to initiation of neoadjuvant therapy. Identification of distant metastases after the start of therapy in cases where pre-therapy evaluation showed no metastases is considered progression of disease. If a patient was designated to have detectable distant metastases (M1) before chemotherapy, the patient will be designated as M1 throughout.

Appendix 6
American Joint Committee on Cancer TNM Classification of Malignant (cont.)

Anatomic Stage/Prognostic Groups^a

Stage	T	N	M ^c
0	Tis	N0	M0
IA	T1 ^c	N0	M0
IB	T0	N1mi	M0
	T1 ^c	N1mi	M0
IIA	T0	N1 ^b	M0
	T1 ^c	N1 ^b	M0
IIB	T2	N0	M0
	T2	N1	M0
	T3	N0	M0
IIIA	T0	N2	M0
	T1 ^c	N2	M0
	T2	N2	M0
	T3	N1	M0
IIIB	T3	N2	M0
	T4	N0	M0
	T4	N1	M0

Appendix 6 American Joint Committee on Cancer TNM Classification of Malignant (cont.)

Stage	T	N	Mc
	T4	N2	M0
IIIC	Any T	N3	M0
IV	Any T	Any N	M1

Reprinted with permission from AJCC: Breast. In: Edge SB, Byrd DR, Compton CC, et al., eds.: AJCC Cancer Staging Manual. 7th ed. New York, NY: Springer, 2010, pp. 347–76.

Note: Stage designation may be changed if postsurgical imaging studies reveal the presence of distant metastases, provided that the studies are carried out within 4 months of diagnosis in the absence of disease progression and provided that the patient has not received neoadjuvant therapy. Post-neoadjuvant therapy is designated with "yc" or "yp" prefix. Of note, no stage group is assigned if there is a complete pathologic response (CR) to neoadjuvant therapy, for example, ypT0cM0.

^a T1 includes T1mi.

^b T0 and T1 tumors with nodal micrometastases only are excluded from Stage IIA and are classified Stage IB.

^c M0 includes M0(i+); The designation pM0 is not valid; any M0 should be clinical. If a patient presents with M1 prior to NAST, the stage is considered Stage IV and remains Stage IV regardless of response to neoadjuvant therapy.

Appendix 7

Correction of Predicted DLCO for Hemoglobin and Alveolar Volume

All DLCO measurements will be obtained as per the American Thoracic Society and European Respiratory Society (ATS/ERS) guidelines (MacIntyre et al. 2005). The predicted DLCO value should be corrected for both hemoglobin (H_b) and alveolar volume (v_a).

Pulmonary function test laboratories that follow the ATS/ERS guidelines should be able to provide the value for DLCO, corrected for v_a . A single breath v_a may be used to obtain DLCO, corrected for v_a . Use the following equation to determine the predicted DLCO, corrected for H_b and v_a :

$$\text{Predicted DLCO, corrected for } H_b \text{ and } v_a = [\text{DLCO, corrected for } v_a] \times [1.7 \times H_b / (9.38 + H_b)]$$

Use the formula below to determine the percentage of predicted DLCO value (now corrected both for H_b and v_a):

$$\% \text{ of predicted DLCO (corrected for } H_b \text{ and } v_a) = [\text{actual DLCO} / (\text{predicted DLCO corrected for } H_b \text{ and } v_a)] \times 100$$

TITLE: **PROTOCOL**
**A PHASE II RANDOMIZED, DOUBLE-BLIND STUDY OF
NEOADJUVANT LETROZOLE PLUS GDC-0032 VERSUS
LETROZOLE PLUS PLACEBO IN POSTMENOPAUSAL
WOMEN WITH ER-POSITIVE/HER2-NEGATIVE, EARLY
STAGE BREAST CANCER**

PROTOCOL NUMBER: GO28888/BIG-3-13/SOLTI 1205/ABCSG 38/ NCT02273973

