Appendix 1 Schedule of Assessments (cont.)

- ^h Two formalin-fixed, paraffin-embedded core needle biopsies and one freshly frozen OCT core needle biopsy are required prior to initiation of treatment (pretreatment) and also on Day 15. A formalin-fixed, paraffin-embedded tumor block from a surgical resection is required at surgery (Weeks 17–18).
- ⁱ Complete blood count includes red blood cell count, hemoglobin, hematocrit, white blood cell count with differential (neutrophils, bands, eosinophils, basophils, lymphocytes, monocytes, and other cells), and platelet count. Screening results may be valid for Week 1, Day 1 if performed within 7 days prior to Week 1, Day 1.
- ^j Fasting (≥ 10 -hour fast) serum chemistry: BUN, creatinine, sodium, potassium, magnesium, bicarbonate, calcium, phosphorus, total protein, albumin, serum bilirubin, alkaline phosphatase, glucose, AST, and ALT. Screening results may be valid for Week 1, Day 1 if performed within 7 days prior to Week 1, Day 1.
- ^k Glucose levels may be obtained by fingerstick. Screening results may be valid for Week 1, Day 1 if performed within 7 days prior to Week 1, Day 1.
- ^l Fasting lipid profile includes total cholesterol, HDL, LDL, triglycerides, amylase, and lipase. Screening results may be valid for Week 1, Day 1 if performed within 7 days prior to Week 1, Day 1.
- ^m Includes specific gravity, pH, glucose, protein, ketones, and blood. Screening results may be valid for Week 1, Day 1 if performed within 7 days prior to Week 1, Day 1.
- ⁿ *DLCO is obtained at screening and prior to surgery. The DLCO test should be repeated if there is clinical suspicion of pneumonitis. DLCO calculations are described in Appendix 7. The hemoglobin value used for correcting DLCO should represent the patient's actual hemoglobin level and should be obtained within 7 days of the DLCO test.*
- ^o *Baseline bone mineral density will be measured via dual-energy X-ray absorptiometry (DXA) and will need to be obtained in women with a history of osteoporosis and/or fractures, or who are at increased risk of osteoporosis. DXA measurement of both the hip and lumbar spine is suggested. When either the hip or lumbar spine is not a valid skeletal site for BMD measurement, then the 33% (one-third) radius should be measured. In some patients, measurement of the hip alone could be sufficient.*
- ^p Pretreatment sample for plasma protein biomarkers should be obtained prior to dosing. Refer to laboratory manual for more information.

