4.1.1 Inclusion Criteria

Patients must meet the following criteria for study entry:

- Signed Informed Consent Form (ICF) prior to any study-specific procedure
- Female patients
- Postmenopausal status and age ≥ 18 years. Postmenopausal status is defined as follows:
 - Age ≥ 60 years or
 - Age < 60 years and 12 months of amenorrhea plus follicle stimulating hormone (FSH) and plasma estradiol levels within postmenopausal range by local laboratory assessment or
 - Prior bilateral oophorectomy (≥ 28 days prior to Day 1 of treatment)
- Histologically confirmed invasive breast carcinoma, with all of the following characteristics:
 - Primary tumor ≥ 2 cm in largest diameter (cT1-3) by MRI. In the case of a multifocal tumor (defined as the presence of two or more foci of cancer within the same breast quadrant), the largest lesion must be ≥ 2 cm and designated as the “target” lesion for all subsequent tumor evaluations.
 - Stage I to operable Stage III breast cancer
 - Documentation confirming the absence of distant metastasis (M0) as determined by institutional practice (in patients where there may be a reasonable suspicion of advanced disease e.g., large tumors, clinically positive axillary lymph nodes, signs and symptoms).
- ER-positive and HER2-negative breast cancer, as per local laboratory or regional definition
- Breast cancer eligible for primary surgery
- Tumor tissue from FFPE core biopsy of breast primary tumor that is confirmed as evaluable for *PIK3CA* mutation status by central histopathology laboratory
- Eastern Cooperative Oncology Group (ECOG) performance status of 0 or 1
- Fasting glucose ≤ 125 mg/dL
- Adequate hematological, renal, and hepatic function, as follows:
 - Absolute neutrophil count $\geq 1500/\mu\text{L}$
 - Platelets count $\geq 100,000/\mu\text{L}$

- Hemoglobin ≥ 9 g/dL
- Serum bilirubin $\leq 1.5 \times$ the upper limit of normal (ULN)
- Patients with known Gilbert's disease who have serum bilirubin $\leq 3 \times$ ULN may be enrolled
- Aspartate aminotransferase (AST), alanine transaminase (ALT), alkaline phosphatase $\leq 1.5 \times$ ULN
- Serum creatinine $\leq 1.5 \times$ ULN or creatinine clearance ≥ 50 mL/min on the basis of the Cockcroft–Gault glomerular filtration rate estimation:

$$\frac{(140 - \text{age}) \times (\text{weight in kg}) \times (0.85)}{72 \times (\text{serum creatinine in mg/dL})}$$

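### Appendix 7 omits the word predicted from the input to its predicted-DLCO equation; with a measured DLCO entered there, percent predicted no longer depends on diffusing capacity

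*Protocol*

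**What the plan says.** In the protocol version whose Schedule of Assessments (Appendix 1) includes DLCO, the test is done at screening and at the Week 16 presurgical visit. Footnote n adds that "The DLCO test should be repeated if there is clinical suspicion of pneumonitis", and that "DLCO calculations are described in Appendix 7". It also asks for a hemoglobin value taken within 7 days of the test.

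Appendix 7 is titled as a correction of predicted DLCO. Its opening paragraph agrees: "The predicted DLCO value should be corrected for both hemoglobin" and VA. The next paragraph drops the word: "Pulmonary function test laboratories that follow the ATS/ERS guidelines should be able to provide the value for DLCO, corrected for" VA, and a single-breath VA may be used to obtain it. Then comes "Use the following equation to determine the predicted DLCO, corrected for" Hb and VA. The right-hand side of that equation is DLCO corrected for VA, without *predicted*, multiplied by 1.7 × Hb / (9.38 + Hb). A second formula divides the actual DLCO by the result and multiplies by 100. The units of Hb are not given.

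**The concern.** The quantity on the left of the first equation is a predicted value. The quantity on the right is described as something the laboratory reports for the patient, and a single-breath VA is something measured in the patient. A site following the text word for word could reasonably enter the measured, VA-corrected DLCO. The percent-predicted formula would then divide the patient's DLCO by a rescaled copy of itself.

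At stake is the reading of a scheduled safety test. DLCO is repeated on suspicion of pneumonitis, and Grade 2 or higher pneumonitis is an immediately reportable event of special interest (section 5.2.3). About 110 sites are planned. If some take the bracket literally and others supply the missing word, the same patient would get different percentages, and only the second set would move with lung function.

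**Working it through.** **Inputs from the protocol**
- Hb factor: f = 1.7 × Hb / (9.38 + Hb) (Appendix 7, first equation).
- Percent predicted = 100 × actual DLCO / (predicted DLCO corrected for Hb and VA) (Appendix 7, second equation).
- Lowest Hb at entry: "Hemoglobin ≥ 9 g/dL" (section 4.1.1).

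**Assumptions, not in the protocol**
- M is measured DLCO, P is the reference predicted DLCO, and g is the multiplier for the VA adjustment. g = 1 (neutral) unless stated, with 0.8 to 1.2 as a range.
- Hb up to 16 g/dL, and VA of 3 to 5 L where needed.

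The protocol gives no worked example, so there is no stated figure to reproduce.

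**Algebra**
- Bracket read as measured DLCO: the denominator is M × g × f, so percent = 100 × M / (M × g × f) = 100 / (g × f). M drops out.
- Bracket read as predicted DLCO: the denominator is P × g × f, so percent = 100 × M / (P × g × f). M stays in.

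**Numbers with g = 1**

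| Hb (g/dL) | f | Measured reading, any M | Predicted reading, M = P | Predicted reading, M = 0.5 P |
|---|---|---|---|---|
| 9 | 15.3/18.38 = 0.832 | 120.1% | 120.1% | 60.1% |
| 12 | 20.4/21.38 = 0.954 | 104.8% | 104.8% | 52.4% |
| 13.4 | 22.78/22.78 = 1.000 | 100.0% | 100.0% | 50.0% |
| 14 | 23.8/23.38 = 1.018 | 98.2% | 98.2% | 49.1% |
| 16 | 27.2/25.38 = 1.072 | 93.3% | 93.3% | 46.7% |

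For a given Hb and g, the two readings agree only when measured DLCO equals reference, which is when there is no loss to detect. Take a patient whose DLCO falls from reference to half of it while Hb goes from 13.4 to 12. The predicted reading goes from 100.0% to 52.4%. The measured reading goes from 100.0% to 104.8%.

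**Effect of the VA adjustment on the measured reading**
- With g from 0.8 to 1.2 and Hb from 9 to 16, the result runs from 100/(1.2 × 1.0717) = 77.8% to 100/(0.8 × 0.8324) = 150.2%, still independent of M.
- If a site takes DLCO corrected for VA to mean DLCO divided by VA, percent = 100 × VA / f. This runs from 300/1.0717 = 280% (VA 3 L, Hb 16) to 500/0.8324 = 601% (VA 5 L, Hb 9).

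**Which reading the appendix's own algebra supports.** f falls below 1 as Hb falls below 13.4. Multiplying a predicted value by f lowers what is expected of an anemic patient, which is coherent. Applying f to a measured value and calling the product predicted has no such meaning.

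**Units.** Hb 12 g/dL entered as 120 g/L gives f = 204/129.38 = 1.577 instead of 0.954, so the unit needs stating.

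**The case against.** The best case for the plan is that a careful reader would supply the missing word. The appendix title, its opening paragraph and the left-hand side of the equation all concern the predicted value. Where the measured value is meant, the second formula calls it actual DLCO. On that reading the formula works, and no stated figure is wrong. This stands: the equation is ambiguous rather than plainly wrong. It does not remove the problem, because the sentences about the laboratory and the single-breath VA leave the measured reading open, and one permitted reading of a prescribed formula gives a number with no meaning.

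Three stronger inferences are tempting, and the documents do not support them.
- *Percent predicted would stay near 100%.* It would not. It moves with Hb and with the VA adjustment, and the per-litre version gives values so implausible that they should prompt a query.
- *The test could not flag pneumonitis.* No percent-predicted threshold appears in the text shown. Footnote n has the test repeated because pneumonitis is already suspected. Table 3 in section 5.1.1.2 lists CT at every grade, with pulmonary function tests only to be considered, alongside imaging. The raw DLCO can still be compared with the patient's own screening value.
- *Comparisons across sites would be invalid.* Section 6.5 names no DLCO analysis and no endpoint shown uses percent predicted, so only a possible loss of comparability follows.

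There is also a limit on what can be seen. Appendix 7 and the DLCO row occur in only one of the two protocol versions supplied, and only the last part of that version is available. The Hb criterion in section 4.1.1 and Table 3 come from the other version, whose schedule has no DLCO row. The missing parts might clarify the term or set a threshold.

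**Conclusion.** The point holds as an internal inconsistency worth correcting. Appendix 7 says that predicted DLCO is to be corrected, then prescribes an equation whose input is not labelled predicted and is introduced as a laboratory value. With a measured value in the bracket, percent predicted equals 100/(g × f) and does not respond to a fall in diffusing capacity. With a neutral VA adjustment this is about 93% to 120% over Hb 16 down to 9 g/dL. With *predicted* in the bracket the formula behaves as intended.

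The cancellation is exact algebra and holds whenever the VA adjustment is a multiplier that does not itself depend on DLCO. The percentages rest on the assumed values of g, the upper Hb and VA. How many sites would take the literal reading cannot be known from the documents, and neither can any effect on patient care.

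**What to change.** In the first equation of Appendix 7, change the bracketed input to *predicted DLCO, corrected for VA*. Make the same insertion in the two sentences before it: the one on what laboratories can provide and the one on the single-breath VA. State that Hb is in g/dL. The second equation can stay as it is.

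The cost is one word in three places and a unit. No visit, test, threshold or clinical rule changes. Recording measured DLCO, predicted DLCO, VA and Hb on the eCRF and calculating percent predicted centrally would be a further safeguard, but it is optional and not needed to correct the error.
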